1. Title: In what way do music-based caregiving influence pain, daily activity, neuropsychiatric symptoms, and medication in patients with dementia?

Protocol approved by the Regional Committees for Medical Research Ethics South East Norway, REK South East at **25.06.2019**

NCT-number NCT04229446
ID: 2018/2519

2. Introduction

The main objective of this study is to evaluate the pain-relieving effect of a well-characterized non-pharmacological treatment program, music-based caregiving (MBC), to patients in nursing homes with dementia and pain. This intervention study will apply for one PhD candidate. Patients with dementia disease will be recruited from eight different nursing homes in Trondheim and Oslo, and each ward will be cluster randomized into intervention - or control wards. Then the health care personnel in the intervention wards will receive education in MBC and perform the intervention during eight weeks. The hypothesis is that this non-pharmacological intervention will reduce pain intensity and improve the activity of daily living (ADL), quality of life (QOL) and general activity, as well as reduce other symptoms in nursing home patients with dementia and pain compared to baseline.

Background

Pain is common in the elderly, and the prevalence of pain increase with age, co-morbidities and frailty 1,2. While the prevalence of pain in older adults in the general population is estimated to range from 25%-50% 2-4, the prevalence of pain in patients living in nursing homes and community care varies from 28% to 87% 5,6. Musculoskeletal pain disorders have been estimated to affect as many as 80% of those above 65 years 7,8. Although almost one fifth of the elderly have symptomatic osteoarthritis 9, most of the chronic pain disorders are of unknown cause 10. Thus opioids are not the best treatment with unclear effect over time and serious side effects (sedation, dizziness, falls, dysphoria, obstipation) in the elderly 11. This knowledge is in contrast to the practice today. In Denmark, 41% of nursing home residents and 28% of home-domiciled patients with dementia use opioids 12.

Previous studies demonstrate that more than 80% of patients in nursing homes in Norway had dementia disease 13,14. Dementia is a syndrome due to disease of the brain, usually of a chronic and progressive nature, in which there is disturbance of multiple higher cortical functions, including memory, reasoning, orientation, comprehension, calculation, learning capacity, language, and judgement 15. Dementia has different stages; mild, moderate and severe dementia. In severe dementia (disease), most of the patients have lost verbal

language and are dependent on of nursing care 15. Patients with dementia also experience many severe neuropsychiatric symptoms. SelbÅk et al 16 followed 931 nursing home patients with dementia over time. Agitation, irritability, disinhibition, and apathy were the most prevalent and persistent symptoms during the study period. Depression and anxiety became less severe over time, whereas the agitation subsyndrome (agitation /aggression, disinhibition, and irritability) and apathy increased in severity during the follow-up period.

Pain is under-reported in the elderly since the elderly or the health care personnel do not report pain, and because of failure of regular and systematic pain assessment in the health care system 17. Pain assessment is challenging in the elderly because of impaired vision and hearing, memory, verbal and cognitive functions, and neuropsychiatric symptoms. If not adequately treated, chronic pain can cause depression, agitation, and aggression in patients with dementia 18. Given the language loss in the most advanced stage of dementia and sometimes after stroke, a cause of dementia, valid and reliable methods for pain assessment in nonverbal older adults are needed 19. MOBID-2, an observation based pain assessment tool, will be used in patients with dementia in the present study. MOBID-2 is validated in nursing homes patients with dementia in Norway 6,20.

Based on current knowledge, non-pharmacological interventions should be the first-line treatment approach for pain in most cases for patients with dementia 18. Since pharmacological treatment for chronic pain is often inadequate and the elderly are prone to

side-effects, more evidence about non-pharmacological treatments is needed, especially for elderly with dementia. Many studies are conducted in this area today, but unstructured and non-evidence based interventions are commonly used 21. Based on current knowledge, non-pharmacological interventions should be the first-line treatment approach for pain in most cases for patients with dementia 18. Since pharmacological treatment for chronic pain is often inadequate and the elderly are prone to side-effects, more evidence about non-pharmacological treatments is needed, especially for elderly with dementia. Many studies are conducted in this area today, but unstructured and non-evidence based interventions are commonly used 21. One of the most common non-pharmacological approaches for treating behavioral and psychological symptoms of dementia is therapeutic use of music 22(. Many of the studies done have low methodological quality with small sample sizes 23, but there seems to be some evidence (for) that non-pharmacological interventions like activity and music can relieve pain 24, depression²⁵ and increase QoL 23. However, more research is needed using controlled studies of high quality 23.

The most convincing evidence of effect when reviewing interventions addressing QOL, discomfort and behavior and psychiatric symptoms in person with dementia comes from functional analysis-based interventions 26. These rely on the nursing home staff to implement a care system, be involved in staff-education, protocol or systematic care planning. Examples of such interventions are the ABC dementia, Serial-trial intervention and (the) TIME 27-29. These interventions prove to be powerful and important systems to structure care-work, deliverance and education, however they are comprehensive systems to implements and not designed to inform on one specific symptom like pain. That is also why there is a shortage of functional analysis-based interventions targeting pain intensity specifically.

The literature suggests that music may also provide effects for pain intensity for patients with dementia 30. However, so far the studies are small, underpowered or performed with less robust methods 31. A review that investigated whether interactive or receptive deliverance (i.e. listening to) of music are more effective to reduce agitation in persons with dementia found evidence that receptive deliverance does reduce agitation compared to

ordinary care, while interactive deliverance of music does not 32. In a recent review on non-pharmacological treatments for individuals with dementia, sensory interventions like music were most effective to reduce agitation followed by interventions targeting pain specifically 33. The evidence might suggest that music reduces stress due to sensory effects and by activating reminiscing.

Physical activity and active training has been investigated in persons with dementia and have been able to prevent falls, improve physical and mental function and also neuropsychiatric symptoms 34. There is currently a dearth of studies to provide information on what interventions have proved to benefit pain intensity, and also looking at effects by age, gender, type and grade of dementia 21. The physiological and psychological effects of music have been thoroughly researched in later years. Precise therapeutic use of music can aid attention, regulate autonomic dysregulation and access latent functional mental resources 35.

Music-based caregiving (MBC) has been developed through a dialogue between neuroscience and clinical research in dementia care since the early 1990s, inspired by the work of Michael Thaut and Linda Gerdner 36,37. Thaut and Gerdner's work has demonstrated the clinical potential and efficacy of neurologic music therapy and individualized music 38. MBC has (been) continually built on neuroscientific research in continuing dialogue with the Center for Biomedical Research at Colorado State University, Berklee School of Music/Harvard Medical School in Boston and the neuroscientific work of Åres Theorell and associates at Karolinska Sjukhuset in Stockholm 39. The PhD project - Integrated music in nursing homes, an approach to dementia care, developed song, music and dance into a systematic approach to dementia care through the period 2000-2012 40.

MBC provides in-depth training on how music, song and movement can be used in caregiving for people with dementia. The program has been developed on behalf of the Norwegian Directorate of Health and is based on neurological music therapy with elements of music therapy and music education, and added to Kompetanseløft 2020.

2.1 Need description

i, · Increased focus on pain and non-pharmacological pain management in a vulnerable group of patients

i, · The non-pharmacological intervention can reduce pain intensity and strengthen ADL, QOL and activity, reduce pharmacological side effects and reduce symptoms in nursing home patients with dementia and pain without side effects.

i, · Relieving pain without side effects will also be valuable for the patient's family.

i, · This study will increase the focus on pain and pain management for health care professionals in nursing homes and the community. The training of the staff in the intervention nursing homes will enhance their clinical skills.

i, · This increased competence can strengthen the motivation for the staff in the care of the patients with dementia, and may reduce the turnover of the staff. Hopefully it can also stimulate their wish for knowledge update.

i, · The health professionals in the intervention group will receive education in a program with music, song and dance with the intention to reduce pain, and strengthen ADL, QOL and activity, reduce side effects and reduce symptoms in nursing home patients with dementia and pain. If the intervention shows effect, the health care professionals in the control nursing homes will retain and, hopefully use, the training after the study is ended.

i, · The research group is multi-professional from different research groups in Norway. All of the nurses, physicians, experts in epidemiology, music therapy, and user participants work together. This collaboration will strengthen the research competence for the group and for the different members.

3. Aims and objectives

The overarching aim of the present study is to extend knowledge about pain in patients with dementia and to evaluate if an intervention with music-based caregiving (MBC) will reduce

pain intensity and improve activity and QoL in nursing home patients with dementia and pain.

The baseline descriptions of pain and pain management in patients with dementia disease in the included nursing homes will be published as a part of another study.

The research questions in the present study are:

1. Will music based caregiving reduce pain and the need for analgesics in patients with dementia in nursing homes?
2. Will music-based caregiving impact on QoL, ADL function, and total daily physical function?
3. Will implementation of music-based caregiving impact on neuropsychiatric symptoms and psychopharmacological medication?

The primary aim is to give better and safer pain management to patients with pain and dementia in nursing homes.

Secondary aims are:

- to increase total daily activity, ADL function, QoL, and reduce neuropsychiatric symptoms, and
- to increase knowledge of pain in patients in nursing homes: the occurrence, intensity, location, treatment, diagnoses, and comorbidities.

4. Project methodology

4.1. Design, method and analysis

This is a cluster-randomized controlled trial including patients with dementia and pain living at different wards at eight nursing homes.

1) Eight nursing homes will be selected to participate, four in Trondheim and four in Oslo.

Both municipalities have accepted the collaboration, and contact has already been

established with randomly selected nursing homes.

2) Subsequently, all patients at the 8 nursing homes will be screened with respect to

dementia and pain (see screening tools later). If patients have dementia and report pain

(â€¥3 on MOBID) they will be included in the study.

3) The included patients will then have a clinical examination of pain and pain management

by an expert physician (see below). Evaluation of the use of analgesics psychopharmacological medication will be performed. Inappropriate medication (both too

much and too little) will be corrected in collaboration with the nursing home doctor.

4) In addition to the clinical examination of pain, we will measure total daily physical

activity, ADL, QOL, and neuropsychiatric symptoms on all included patients (see below).

5) After the pre test - a randomization of the wards into intervention wards or control wards

will be performed.

6) About 5 staff members at each of the wards randomized to the intervention group will

receive education in the MBC before intervention (see below).

7) As a post-test three month after the intervention has ended, pain, total daily physical

activity, ADL, QOL, and neuropsychiatric symptoms will be measured.

This design facilitates the measurement of the outcome variables in nursing homes patients

before and after the intervention, and between the two groups. The results from the pre- and

post-tests will be compared between the groups to assess whether or not the intervention has

effects on the outcome variables when adjusting for baseline levels (pre-test). This approach

will allow us to evaluate whether changes in the outcome measure are caused by the

intervention or other elements.

Participants

In total, 240 patients with dementia and pain (120 from nursing homes in Trondheim and 120 from nursing homes in Oslo) will participate in the study. Contact is already established with nursing homes that will participate both places. Patients will be included if they report moderate pain or more (≥3 on MOBID) and mild dementia or more (≥1 on CDR). They will not be included if they have lived in the nursing home less than four weeks, have short (less than eight weeks) expected lifetime (judged by the nurses), and if they do not understand the Norwegian language. Anonymous data will be collected for comparing patients not included with those included, and the reasons for why they were not included will be described. Before inclusion in the study, patients or their relatives should give an informed consent.

Clinical examination

All the included patients will be clinically examined by expert physicians in the same way as performed in the HUNT3 study 10. Focal pain conditions will be diagnosed according to the 10th revision of the International Statistical Classification of Diseases and Related Health Problems 41, either as a disease diagnosis, or, if no cause of the pain can be identified, by a pain/symptom diagnosis. In addition, the physician will make a critical evaluation of their analgesic and other medications as mentioned above. If medications are inadequate, obviously give side effects, or are in violation with current guidelines, the recommendation for

correction will be given to the physician at the nursing home. This procedure will particularly be the case for all patients having a pain state of known origin with documented effect of specific medication (i.e. osteoarthritis or neuropathic pain).

Education of the health care professionals

After pre-test including clinical examination, a randomization of the wards into intervention wards or control wards will be performed. About 5 staff members at each of the wards randomized to the intervention group will receive education in the MBC. Approximately 60 employees will receive training in MBC by [name] and [name] with a 5-day training course. This training will facilitate the intervention in the way that the health professionals in the intervention group will be competent in applying active (song, dance) and passive (music listening) modalities in individualized music with groups and individuals as needed, mindful of personal preference and dignity and aware of the sensory environment.

Quality of Life in Late-Stage Dementia (QUALID) measures QOL in patients with severe dementia based on information and observations from nurses about the patient's emotions and behavior. The scale has been validated in a Norwegian nursing home population, showing satisfactory psychometric properties 47,48.

Dementia Quality of Life (DQoL). Because QUALID-scale is an observation scale, and there is a lack of studies comparing self-reported and observations QoL in those with dementia, we want to compare the observation estimate with self-report for patients with none, mild and moderate dementia (DQoL). DQoL consists of five domains: self-esteem, positive affect/humor, feeling of belonging, and sense of aesthetics and negative affect. The instrument is evaluated in those with mild and moderate dementia and is used in nursing homes in Norway 49.

Barthel's Activities of Daily Living Index (ADL) is a screening instrument for patients' daily life functioning. This 10-point scale measures patients' degree of self-reliance with a total score ranging from 0 to 20. Lower scores indicate greater dependence on nursing care 50.

The total daily physical activity using two 3-axis accelerometers (Axivity, UK) attached to the skin on the right thigh and low back for 7 continuous days. By utilizing state-of-the-art machine-learning techniques, we have developed a preliminary activity recognition model for lying, sitting, standing, walking and other activities. This model is being used in the Nord-Trøndelag health study (HUNT4). Specifically, the model captures walking velocity and transitions between postures and activities (e.g. sit-to-stand) and sleep quality/duration.

Neuropsychiatric symptoms and depression

The Neuropsychiatric Inventory (NPI-NH) measure 12 different psychiatric symptoms and behavioural disturbances in nursing home residents: delusions, hallucinations, dysphoria, anxiety, agitation/aggression, euphoria, disinhibition, irritability/lability, apathy, aberrant motor activity, sleep and night-time behaviour disorders, appetite and eating disorders. The

screening question is asked to determine if the behavioural change is present. If a screening question is present, there will be sub-questions about frequency (score 1 to 4) and intensity (score 1 to 3) for each behavior. Total score for each behavior is from 1 to 12. The scale has been validated for patients in nursing homes in Norway 51.

Cornell scale for depression in dementia assesses signs and symptoms of major depression in patients with dementia in an interview with the health care providers. The scale consists of 19 items in five domains based on observation of behaviour 52. Each question is scored on a two-point scale: 0=absent; 1=mild or intermittent; 2=severe; n/a = unable to evaluate 2.

Sample size

A power calculation was performed on MOBID-2. Based on the literature review we assumed the mean difference to be 1.2 and the common standard deviation to be 3. To keep statistical power of 80% ($\beta = 0.2$) and significance level of 5%, we would need 100 in each group to reveal the anticipated difference between the groups as statistically significant. Taking in consideration the possible cluster effect of 20% we aim to enrol 120 patients in both groups 20,53,54.

Statistical analyses

Participants' background characteristics will be described as means and standard deviations (SD) for normally distributed continuous data or medians and range for continuous data with skewed distributions. Categorical data will be presented as counts and percentages. At the pre-test, possible between-group differences will be assessed using independent samples t-tests

when comparing pair of normally distributed continuous variables, chi-square test for categorical variables and Mann-Whitney test for continuous variables with skewed distribution. Possible differences between the groups concerning the mean MOBID-2 Pain Scale, QoL, ADL, total daily physical activity, and neuropsychiatric symptoms scores over time and at given time points will be estimated with linear random intercept quantile mixed-effect models. Mixed model regression modelled with linear random intercept permits multiple measurements per person over time, irregular intervals between measurements and allows for incomplete data on assumption that data are missing at random 55. A significance level of 5 % will be considered statistically significant for all analyses. Data will be analyzed using IBM Statistical Package for the Social Sciences (SPSS) version 23.

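### The random-intercept model puts one variance on pre- and post-test pain; if the pre-test is the screening score, cut at 3, the post-test arm difference probably gets too small a standard error

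*Combined protocol and SAP*

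**What the plan says.** All places are in section 4.1 of the combined protocol and SAP.

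- **Model (Statistical analyses).** Arm differences in mean MOBID-2 and the other "scores over time and at given time points will be estimated with linear random intercept quantile mixed-effect models". The next sentence describes a mixed regression with a linear random intercept that allows repeated measurements per person. The available text gives no residual covariance structure, no time-specific variance and no robust standard error.
- **Selection (Participants).** "Patients will be included if they report moderate pain or more (≥3 on MOBID"). Step 2 of the numbered design list applies this rule at screening.
- **Timing (numbered steps).** Step 4 lists what is measured besides the clinical pain examination: activity, ADL, QoL and neuropsychiatric symptoms. It describes no second MOBID-2 before randomization. Step 7 measures pain again at one post-test, three months after the intervention ends.
- **Baseline.** The text after step 7 says that the comparison takes the pre-test level into account, but not how.
- **Sample size.** "we assumed the mean difference to be 1.2 and the common standard deviation to be 3". One SD is used. The text does not say whether it refers to the pre-test, the post-test or the change.

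**The concern.** A random intercept with a single residual variance implies the same total variance at every time point. Selecting patients on a minimum pre-test score removes the lower part of that distribution, while the post-test is free to spread below 3. The two variances should then be expected to differ, with the pre-test the smaller. The model averages them and applies the average to the arm difference at the post-test. If the post-test variance is the larger, the confidence interval for that difference is too narrow and the false-positive rate exceeds the stated 5%.

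MOBID-2 is the measure on which the trial is sized. The plan promises contrasts both over time and at given time points without ranking them, so the affected contrast is one of those that may be reported for pain.

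**Working it through.** **1. The plan's own figure.** With difference 1.2, SD 3, two-sided 5% and 80% power, n per arm = 2 × (1.96 + 0.84)² × 3² / 1.2² ≈ 98, and 99 with the t distribution. The plan states 100, so it reproduces. Then 100 × 1.2 = 120 per arm, as stated. The calculation uses one common SD and does not touch the pre/post question.

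**2. What the model does.** Take two time points, complete data, n per arm, and arm-by-time means. The REML total variance is (V_pre + V_post)/2. Hence:

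- model SE of the post-test difference = √[(V_pre + V_post)/n]
- correct SE = √[2·V_post/n]
- ratio = √[(V_pre + V_post)/(2·V_post)]
- actual type I error = 2 × [1 − Φ(1.96 × ratio)]

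**3. Check against a fitted model.** One simulated data set with 120 per arm had SDs of 1.861 (pre) and 2.438 (post).

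- Fitted person variance plus residual variance: 1.768 + 2.935 = 4.703. Average of the two variances: (3.463 + 5.943)/2 = 4.703.
- Model SE of the post-test difference: √(2 × 4.703/120) = 0.280, the same as from the fit. Correct SE: √(2 × 5.943/120) = 0.315. Ratio 0.89.
- SE of the difference in change from the same fit: 0.313. This contrast uses only the within-person differences, so pooling the two variances does not distort it.

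**4. Direction.** Suppose scores before selection are normal with equal variance σ² at both times and correlation ρ, and selection cuts the pre-test variance to σ²(1 − δ). The post-test variance becomes σ²(1 − ρ²δ), which is larger for any ρ below 1. With mean 3, σ = 3, cut at 3 (δ = 2/π = 0.637) and ρ = 0.5, the pre-test SD is 3√(1 − 0.637) = 1.81 and the post-test SD is 3√(1 − 0.25 × 0.637) = 2.75. The ratio is 0.85 and the type I error 9.7%. This version lets pain scores fall below 0, so it shows direction and overstates size.

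**5. Size with bounded scores.** Assumptions, none of them in the documents: integer scores from 0 to 10, the screening score used as pre-test, no arm effect, no ward effect, 120 per arm, 4,000 simulated trials per row.

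| Mean, SD before selection | Correlation | Fall by post-test | SD pre | SD post | SE ratio | Type I error |
|---|---|---|---|---|---|---|
| 2, 3 | 0.5 | 0 | 1.68 | 2.48 | 0.85 | 9.9% |
| 3, 3 | 0.5 | 0 | 1.84 | 2.58 | 0.87 | 8.9% |
| 3, 3 | 0.5 | 1 | 1.84 | 2.46 | 0.88 | 8.3% |
| 4, 2.5 | 0.5 | 1 | 1.76 | 2.24 | 0.90 | 7.9% |
| 4, 3 | 0.7 | 1 | 1.99 | 2.47 | 0.90 | 7.9% |
| 5, 3 | 0.5 | 1 | 2.12 | 2.65 | 0.90 | 7.7% |

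Over means 1 to 5, SD 2.5 to 3 and correlation 0.3 to 0.7, the ratio is about 0.85 to 0.93 and the type I error about 7% to 10%.

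**6. Alternatives under the same type of simulation.**

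- Difference in change: SE ratio 0.98 to 1.01, type I error 4% to 6%.
- ANCOVA on the post-test: SE ratio 0.99 to 1.00, type I error about 5%.
- Fresh pre-test after screening (mean 3, SD 3): ratios 1.02, 1.00 and 0.93, type I errors 4.6%, 4.9% and 6.8%, for screening/pre-test correlations of 0.5, 0.7 and 0.9.
- Large fall in post-test pain, with scores piling up at 0: ratio 0.94 to 0.99, type I error 5.1% to 6.3%.

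**The case against.** The strongest reply is that the plan may not commit to the affected analysis.

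- **Baseline adjustment is announced.** If it means the pre-test as a covariate for the post-test, the problem disappears. This stands in part: the form is not stated, and the Statistical analyses text describes a repeated-measures model, not an ANCOVA.
- **The change contrast is sound.** It is among the promised comparisons and is correct with complete data. This stands, but the plan does not make it the primary contrast.
- **The quoted sentence names a quantile model.** The variance formula above does not govern its standard errors. This stands, so the point applies only to the linear random-intercept reading. That reading is supported by the next sentence and by the stated target, the mean score.
- **Silence on residual variances is not a choice of equal ones.** A random intercept with time-specific residual variances would be adequate, and the wording does not exclude it. It does not specify it either.
- **The screening score may not be the pre-test score.** The documents never say that it is. This is the most important condition on the result.
- **A floor is plausible.** Both arms have their analgesic treatment reviewed, and pain may fall far enough to compress the post-test spread.

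A reader might infer that the 5% level is lost in any event, or that the error rate reaches 12%. The documents support neither. The change contrast, ANCOVA, several fresh-pre-test cases and some floor cases stay near 5%. The 12% needs unbounded normal scores with mean 1 and SD 3, which puts about 37% of them below zero. It also treats the plan's SD of 3, given for the trial groups, as the SD of unselected residents.

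**Conclusion.** The point holds as a conditional weakness of the stated method. If the linear random-intercept model is fitted with one total variance, and the screening MOBID-2 serves as the pre-test, the standard error of the post-test arm difference in pain is probably too small. It is then about 0.85 to 0.93 of the correct value, with a type I error of about 7% to 10% instead of 5%.

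These figures rest on assumed means, SDs, correlations and score limits, because the documents give no pre- or post-test SDs. They leave out ward clustering, so they isolate the variance issue. They do not show that the trial's pain result as a whole would be invalid. The inclusion rule gives a concrete reason to doubt equal variances, and the plan should not rely on them when the remedy is this simple.

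**What to change.** In section 4.1, Statistical analyses, specify one of the following for MOBID-2, with any ward effect added on top:

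1. a linear model for the mean score with an unstructured pre/post covariance (separate pre-test and post-test variances and one covariance), from which the post-test arm difference is taken; or
2. a linear model for the post-test score with the pre-test score as covariate, which also gives a definite form to the baseline adjustment announced after step 7.

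Remove the word quantile if the mean is the target. State in the numbered steps whether the pre-test MOBID-2 is the screening score or a new measurement.

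The cost is a line of wording and, for option 1, one extra variance parameter. No new data or patients are needed. The post-test interval may become wider: in the fitted example the SE goes from 0.280 to 0.315, about 12% more (0.315/0.280 = 1.125), which is the width it should have had.

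### Wards are randomised, but the planned analysis has no ward term, so between-group standard errors will be too small if patients in the same ward are correlated

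*Combined protocol and SAP*

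**What the plan says.** The introduction states that "each ward will be cluster randomized into intervention - or control wards", and section 4.1 describes the design in the same terms: "This is a cluster-randomized controlled trial including patients with dementia and pain living at different wards at eight nursing homes". The Sample size text allows for this: "Taking in consideration the possible cluster effect of 20% we aim to enrol 120 patients in both groups".

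The Statistical analyses text then says that group differences in "scores over time and at given time points will be estimated with linear random intercept quantile mixed-effect models". It explains the choice of model as follows: "Mixed model regression modelled with linear random intercept permits multiple measurements per person over time". It mentions no ward or nursing-home effect, cluster-robust variance or degrees of freedom based on wards. The pre-test comparisons use independent-samples t, chi-square and Mann-Whitney tests, which also take patients as independent. Earlier in section 4.1 the plan says that the between-group comparison of pre- and post-test results will adjust for baseline levels.

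The number of wards is not stated. The paragraph on staff education gives two figures from which it can be inferred: "About 5 staff members at each of the wards randomized to the intervention group will receive education in the MBC" and "Approximately 60 employees will receive training in MBC".

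**The concern.** Patients in one ward share staff, routines and raters, so their scores tend to be correlated. When the ward is randomised, that correlation adds to the variance of the group difference. A patient-level random intercept captures correlation between a patient's own repeated measurements, but not correlation between patients in the same ward. A model with only that intercept therefore understates the standard error, and a chance difference between wards can be reported as an effect of music-based caregiving. The plan allows for clustering in its sample size but not, in the text available, in its test. This affects pain and every other outcome listed for the same model.

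**Working it through.** **The plan's own figure.** Inputs from Sample size: difference 1.2, SD 3, power 80%, alpha 5% (two-sided assumed). n = 2 × (1.96 + 0.84)² × 3² / 1.2² gives 99 per group, or 100 with the t distribution. Then 100 × 1.2 = 120. The stated figures reproduce if the 20% is read as a design effect (DE) of 1.2.

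**Ward size (inferred).** About 60 staff at about 5 per ward gives 60 / 5 = 12 intervention wards. With 120 patients per group, 120 / 12 = 10 per ward, and equal allocation gives about 24 wards.

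**Follow-up comparison ignoring ward.** DE = 1 + (m − 1) × ICC with m = 10. The true standard error is √DE times the model's, so type I error = 2 × [1 − Φ(1.96 / √DE)].

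| Case | DE | Type I error |
|---|---|---|
| 20% read as DE 1.2 (ICC 0.2 / 9 = 0.022) | 1.20 | 7.4% |
| ICC 0.05 (assumed) | 1.45 | 10.4% |
| ICC 0.10 (assumed) | 1.90 | 15.5% |
| 20% read as ICC 0.20 | 2.80 | 24.1% |

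At ICC 0.05, 16 wards give 13.3% and 32 wards give 8.9%.

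**Baseline-adjusted and group-by-time tests.** These depend on how stable ward effects are. They were simulated with 24 wards of 10, pre and post, patient correlation within ward 0.5 (assumed), no treatment effect and 12,000 runs per cell. Type I error at ICC 0.022 / 0.05 / 0.10:

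| Correlation of ward effects, pre to post | Baseline-adjusted | Group-by-time |
|---|---|---|
| 1.0 | 5.9 / 6.3 / 8.2% | 5.2 / 5.1 / 5.1% |
| 0.8 | 6.2 / 8.1 / 11.5% | 6.0 / 7.2 / 9.6% |
| 0.5 | 7.6 / 10.5 / 15.4% | 7.6 / 10.9 / 15.4% |

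Ward-level tests on the same data stayed at 4.8–5.4%.

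**Medians.** The plan names a quantile model. For a difference in medians at follow-up, using the standard error valid for independent patients, the variance ratios are 1.14 / 1.30 / 1.59 and the type I errors 6.6 / 8.6 / 12.1% (60,000 runs). A packaged median regression with its default standard error was conservative without clustering (3.2%) and rose to 4.5 / 6.6 / 9.6% (2,000 runs). No quantile mixed model was fitted.

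**Does a plain ward intercept suffice?** In five simulated datasets (ICC 0.10, ward correlation 0.5), adding a constant ward intercept left the group-by-time statistic unchanged to within 0.001 (2.326 in the first dataset, with and without it). Adding a ward-by-time effect reduced it (1.692 in that dataset), matching the t statistic for ward-level mean change.

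**The case against.** **The level of the random intercept is never stated.** The sentence about repeated measurements describes what mixed models can do and does not exclude a ward intercept. That is true, but the patient is the only unit named. A constant ward intercept would in any case leave the group-by-time test uncorrected.

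**Most of the sizes rest on assumptions.** The ICCs of 0.05 and 0.10, the ward size and the correlations over time are not in the plan. Only the 7.4% follows from the plan's own number, and only under one reading of it. This stands as a limit on size. The direction needs only an ICC above zero, which the plan's 20% allowance already anticipates.

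**The named quantile model was not tested.** This also stands. The packaged median regression gave 4.5% at ICC 0.022, below nominal. Its error still rose with clustering from a conservative 3.2%, so the low figure reflects a conservative standard error and not protection against ward effects.

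**Baseline adjustment may mean the group-by-time contrast, which is safe when ward effects are constant.** The Statistical analyses text names no baseline covariate, so this reading is possible. Constancy is doubtful, though: trained ward staff deliver the programme, partly in twice-weekly groups. If ward effects change only in intervention wards, the group-by-time error is smaller: 5.5 / 6.1 / 7.2% at correlation 0.8 and 6.2 / 7.6 / 10.6% at 0.5, for the same three ICCs. Control wards also have reason to change, since analgesic treatment is revised in both groups. The time-point comparisons are affected on any reading.

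**Conclusion.** The concern holds. As written, the analysis leaves out the unit of randomisation. For a follow-up comparison of means, the true type I error is about 7.4% at the plan's own allowance (read as a design effect of 1.2) and roughly 10–16% at ICCs of 0.05–0.10 with about 10 patients per ward. Baseline-adjusted comparisons run from about 6% to 15% over the same ICCs, depending on how stable ward effects are. Group-by-time tests run from no inflation with constant ward effects to about 15% at a correlation of 0.5. Median comparisons are affected less. The omission itself is clear from the text; the size of the inflation is not fixed by the documents. The part of the document between Statistical analyses and section 4.3 was not available for this check, so the finding covers the remaining text.

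**What to change.** State that every between-group analysis accounts for ward, by one of:

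- a follow-up model adjusted for baseline, with a ward random intercept;
- a repeated-measures model with patient and ward random effects that includes a ward-by-time effect;
- a ward-level analysis of mean change.

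For a mean-based mixed model, specify Satterthwaite or Kenward-Roger degrees of freedom. With 24 wards these are about 24 − 2 = 22, or 21 with city in the model, or 22 − 7 = 15 with the eight nursing homes as fixed effects (usable only if each home has wards in both arms). If the quantile model is kept, obtain standard errors by resampling whole wards. State the number of wards, say what the 20% represents, and report the ward ICC.

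The cost is wording, slightly more analysis work and wider intervals. For a follow-up comparison with SD 3 and 120 per group, the unclustered 95% half-width is 1.96 × 3 × √(2/120) = 0.76. With t(22) = 2.074 and the factor √DE it becomes 0.88 at DE 1.2, 0.97 at ICC 0.05 and 1.11 at ICC 0.10, against the planned difference of 1.2. Power (normal approximation) is 80.7%, 73% and 61% in the same three cases, compared with an apparent 87% when clustering is ignored. The wording can be changed without altering the design or data collection.
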